7.4 Secondary Safety End Points

Comparison of the incidence of all adverse events that occur during the intra-operative and postoperative periods between the two study arms.

To evaluate and compare the incidence of elevated IOP (IOP spikes) in the immediate postoperative period in both study arms. For this study, an IOP spike will be considered an increase of 10mmHg or more from baseline (21). However, all measurements will be collected and analyzed.

8.0 Study Claim

The safety of the Ex-PRESS™ is superior and efficacy as good as trabeculectomy in open angle glaucoma patients.

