1.0 Investigational Plan

A multicenter clinical research study will be conducted in the United States and Canada. A total of 120 subjects will be enrolled with 60 subjects in each arm to compare the safety and efficacy of the Ex-PRESS mini glaucoma shunt implantation versus trabeculectomy in patients suffering from glaucoma.

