5.1 Clinical Studies

Since the Ex-PRESS mini glaucoma shunt was FDA approved, post marketing studies were performed and presented in paper publications and meetings (1, 6-20). The Ex-PRESS was found to be safe and effective in the treatment of glaucoma subjects. A prospective randomized study comparing the Ex-PRESS to trabeculectomy in open angle glaucoma patients was performed in the Netherlands. A total of 40 subjects with primary open angle glaucoma were enrolled in each study arm and followed for 1 year. The Ex-PRESS implant under a scleral flap was found to have a more effective success rate, % IOP reduction and medication reduction compared to trabeculectomy (20).

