7.0 Study Objective

The study objective is to compare the safety and effectiveness of Ex-PRESS implantation under a scleral flap versus trabeculectomy.

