7.1 Primary Effectiveness End Points

The primary effectiveness measure will be qualified and complete success rate defined as $IOP \leq 18 \text{ mmHg}$ with or without medications in the test group as compared to complete and qualified success rate in the concurrent control group at 12 months.

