9.7 Study Withdrawal

All subjects have the right to withdraw at any point during the treatment without prejudice. The investigator can discontinue any subject at any time if medically necessary. If a subject withdraws prematurely from the study, a genuine effort must be made to determine the reason(s) why the subject discontinued the study. The reason must be recorded.

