12.0 Statistical Analysis

The data provided from this randomized controlled study are intended to provide a reasonable assurance of safety and effectiveness for the Ex-PRESS mini shunt compared to standard trabeculectomy.

The primary safety and effectiveness end points are provided in sections 7.1-7.4 of this protocol. The data will be analyzed using the Fishers exact test p-value and Student's paired *t* test p-value comparison. Success rate will be analyzed using Kaplan-Meier survival analysis curves. [Phakic and pseudophakic patients will be explored as a possible covariate in the efficacy and safety analysis.](#)

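### Section 8.0 claims efficacy *as good as* trabeculectomy, but section 12.0 gives no margin, confidence interval or decision rule by which that claim could be reached

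*Combined protocol and SAP*

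**What the plan says.** Section 8.0 makes two claims of different kinds in one sentence: "The safety of the Ex-PRESS™ is superior and efficacy as good as trabeculectomy in open angle glaucoma patients". The safety part is a superiority claim. The efficacy part is a claim of similarity, or at least of not being worse.

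Section 7.1 sets the primary effectiveness measure as success (IOP of 18 mmHg or less, with or without medication) "in the test group as compared to complete and qualified success rate in the concurrent control group at 12 months". Section 7.0 is neutral: "The study objective is to compare the safety and effectiveness of Ex-PRESS implantation under a scleral flap versus trabeculectomy".

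Section 12.0 holds the whole analysis plan. It says "The data will be analyzed using the Fishers exact test p-value", adds a paired t test p-value, and then gives success its own sentence: "Success rate will be analyzed using Kaplan-Meier survival analysis curves". It also names lens status as a covariate to explore. It states no margin, alpha, confidence interval, null hypothesis or rule for reaching the efficacy claim, and no other section available for review does so. Section 12.0 shows no redaction.

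On size, section 1.0 says "A total of 120 subjects will be enrolled with 60 subjects in each arm", without a derivation.

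**The concern.** A test of difference can show that two arms differ. Failing to show a difference does not show that they are alike, least of all with 60 per arm. A claim that one treatment is as good as another, whether read as non-inferiority or as equivalence, needs a stated deficit that is too large to accept and an interval that excludes it. Section 12.0 has neither.

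The gap falls where the wording of section 8.0 expects the result to fall. If the two procedures succeed equally often, the Fisher result will almost always be non-significant, and the plan does not say what may then be concluded. The decision would be made after the data are known, in an unmasked trial, on the primary effectiveness endpoint.

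**Working it through.** **Inputs from the documents.** 60 subjects per arm (sections 1.0 and 9.3.1); a binary month-12 endpoint (section 7.1); Fisher's exact test and Kaplan-Meier curves (section 12.0). The plan gives no calculation to reproduce.

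**Assumptions, because the documents give no figures.** Two-sided alpha 0.05; control success of 60 to 95%; 60 evaluable per arm, or 54 after 10% loss (60 × 0.9 = 54). Some loss is foreseeable, since "All subjects have the right to withdraw at any point during the treatment without prejudice". Applying Fisher to section 7.1 is an inference: section 12.0 refers back to sections 7.1-7.4, and the test fits a binary comparison of two arms.

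**Step 1. How often is Fisher non-significant?** Sum over all outcome pairs (x, y) with Fisher p > 0.05:

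P = Σ Bin(x; n, p_E) × Bin(y; n, p_T)

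where p_E and p_T are the true success rates on Ex-PRESS and trabeculectomy. With n = 60:

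| Control success | Equal | Ex-PRESS 15 points worse |
|---|---|---|
| 60% | 96.8% | 67.7% |
| 70% | 96.9% | 67.6% |
| 80% | 97.2% | 62.5% |
| 90% | 97.8% | 50.6% |
| 95% | 98.9% | 37.3% |

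Over the whole range, a device 15 points worse gives a non-significant result in 37 to 68% of trials (44 to 74% with 54 per arm).

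**Step 2. How often would Fisher settle the claim by favouring Ex-PRESS?** With 60 per arm: 0.5 to 1.6% of trials if the arms are equal, 6 to 9% if Ex-PRESS is 5 points better, and 15 to 56% if it is 10 points better (control 60 to 90%).

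**Step 3. One possible result.** Trabeculectomy 51/60 = 85%, Ex-PRESS 45/60 = 75%, difference -10 points. Fisher p = 0.254. The Wilson 95% limits are 0.7389 to 0.9190 and 0.6277 to 0.8422. The Newcombe limits are:

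- Lower: -0.10 - √[(0.75 - 0.6277)² + (0.9190 - 0.85)²] = -0.10 - 0.1404 = -0.240
- Upper: -0.10 + √[(0.8422 - 0.75)² + (0.85 - 0.7389)²] = -0.10 + 0.1444 = +0.044

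The p-value alone hides that a deficit of up to 24 points is not excluded.

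**Step 4. What an interval rule does.** Suppose the claim is made only if the lower Newcombe limit lies above -M. With M = 15 points, used purely as an illustration, a device truly 15 points worse passes in 2.5 to 2.8% of trials with 60 per arm.

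**Step 5. Which margins this size supports.** Smallest M with 80% power, arms truly equal, by exact enumeration of the Newcombe rule:

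| True success | 60 evaluable per arm | 54 evaluable per arm |
|---|---|---|
| 90% | 16.3 points | 17.25 points |
| 85% | 18.7 points | 19.55 points |
| 80% | 20.3 points | 21.5 points |

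As a cross-check, the normal approximation (1.96 + 0.84) × √[2p(1 - p)/60] gives 15.3, 18.3 and 20.5 points, so the picture does not depend on the interval method.

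**The case against.** **The test is not assigned.** Section 12.0 gives success rate to Kaplan-Meier and mentions Fisher only in general terms; Fisher also fits the incidence comparisons in sections 7.3 and 7.4. This stands, and every Fisher percentage above carries that caveat. It does not close the gap, because the Kaplan-Meier sentence names only curves. An interval for the month-12 difference could be derived from them, but the plan does not say that it will be.

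**A significant result could carry the claim.** A Fisher result favouring Ex-PRESS would support efficacy as good as the control, and the earlier randomized study in section 5.1 makes that possible: the device "was found to have a more effective success rate, % IOP reduction and medication reduction compared to trabeculectomy". This also stands, so a reader should not infer that the plan can never support its claim. But superiority is not the efficacy claim made, and Step 2 shows that even a true 10-point advantage would often be missed.

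**No one says that non-significance will be read as success.** This is the most tempting stronger reading: that the sponsor plans to treat p > 0.05 as proof of similarity. The documents do not say so. The 37 to 68% figure shows what that reading would cost if it were adopted; it does not describe a planned inference.

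**The phrase appears once.** Other sections only compare the arms, and the design is never labelled non-inferiority or equivalence. A reader might infer a failed non-inferiority design or an inadequate sample size. Neither follows, because without a margin the size cannot be judged. The objection makes the cure easier, but section 8.0 remains the trial's stated claim.

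**Conclusion.** The concern holds as an undecided claim. Section 8.0 promises a conclusion for which section 12.0 supplies no rule, unless Ex-PRESS is significantly better. A non-significant p-value cannot stand in for that rule: at 60 per arm, a true 15-point deficit would go undetected by Fisher in 37 to 68% of trials.

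The omission is read directly from the text and needs no assumption. The percentages rest on assumed alpha, success rates and attrition, and on Fisher being the test applied to section 7.1.

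The severity lies between should-fix and must-fix. The gap concerns the stated claim on the primary effectiveness endpoint, but wording can cure it.

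**What to change.** In section 12.0 add text to this effect:

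> The primary efficacy analysis is the difference in month-12 success proportion, Ex-PRESS minus trabeculectomy, by assigned arm, with a two-sided 95% confidence interval (Newcombe). Kaplan-Meier curves are supportive. A non-significant test of difference will not be read as support for the efficacy claim in section 8.0.

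Newcombe is one suitable interval among several; what matters is that it is named in advance. Then choose one of two routes:

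- **(a) Keep the claim.** Conclude *as good as* only if the lower limit lies above -M, with M justified on clinical grounds and fixed before outcome data are examined. Use Step 5 only afterwards, to check whether that M is feasible.
- **(b) Weaken the claim.** If no such M can be justified at this size, replace the efficacy part of section 8.0 with estimation of the difference and its 95% interval.

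The difference test can stay for the safety-superiority claim.

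**Cost.** Route (b) needs wording only, and the price is a weaker claim. Route (a) needs a clinical justification and, at the present size, a wide margin: about 16 to 20 points with 60 evaluable per arm and about 17 to 21.5 with 54, at 90 to 80% success. A tighter margin would cost patients. By the same rule, 80% power at 15 points needs 69, 92 or 112 evaluable per arm at 90, 85 or 80% success.

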9.0 Study Protocol

9.1 Study Synopsis

Title:	A prospective randomized multi-center study to compare the Ex-PRESS™ to trabeculectomy in patients with open angle glaucoma who failed medical treatment and for which filtering surgery is indicated
Protocol Number:	XVT-01
Number of Sites:	7 sites were approved.
Study Period:	2 year, 10 visits: Pre-operation, day of surgery, day 1, 1-2 Weeks, Months 1, 3, 6, 12, 18 and 24 post operation. Additional visits will be performed and recorded as required for the optimal treatment and follow up of the patient. Additional visits are defined as visits that were not preplanned and considered emergent.
Study design:	A prospective, two arm, active control, unmasked, randomized study
Objectives:	A prospective randomized trial to compare the safety and efficacy of the Ex-PRESS to trabeculectomy in patients with open angle glaucoma who failed medical or are allergic to medical treatment and for which filtering surgery is indicated
Control Arm	Subjects undergoing trabeculectomy with the use of Mitomycin C
Treatment Arm	Subjects undergoing Ex-PRESS Under Scleral Flap implantation procedure with the use of Mitomycin C
Subject Population:	Open angle glaucoma patient's candidates for filtering surgery. The patients may have a history of cataract phacoemulsification surgery.
Sample Size:	Total of 120 subjects with 60 subjects in each arm. Each site can enroll a maximum of 30 subjects and a minimum of 5 subjects for each study arm.
Follow-up duration:	2 years
Target enrollment period:	Up to 1 year

9.2 Study Device

The Ex-PRESS R version miniature glaucoma shunt.

9.3 Study Population

9.3.1 Number of Subjects

A total of 120 subjects will be enrolled into the study with 60 subjects in each arm.

9.3.2 Study Population

The study population will consist of subjects diagnosed with open-angle glaucoma (OAG) (which includes pseudoexfoliative and pigmentary glaucoma) and subjects diagnosed with ocular hypertension (OHT). Subjects must be currently taking ocular hypotensive medications or found to be allergic to hypotensive medications. Subjects may also have a history of cataract phacoemulsification surgery.

All subjects will have IOP of 19mmHg or more. For example, a subject who is currently taking two medications and has a pressure of 21mmHg with cataract phacoemulsification surgery performed 12 months before will qualify for enrollment in the study. A complete listing of inclusion and exclusion criteria is presented in section 9.3.3 below.

9.3.3 Inclusion Criteria

- Adult subject over the age of 18
- Subject diagnosed with open angle glaucoma (POAG, PXFG or PDSG) or ocular hypertension
- Subject is a candidate for filtering surgery with intra-operative anti-metabolites
- IOP > 18 mmHg on maximum tolerated medical therapy based on two measurements taken 1 hour apart at the same visit.
- Subject willing to attend all follow-up evaluations
- Subject willing to sign informed consent.

9.3.4 Exclusion Criteria

- Subject diagnosed with: PACG, NTG, secondary glaucoma, neovascular glaucoma
- Subject has history of glaucoma surgery (filtering, glaucoma drainage device, cyclo destructive procedures)
- Subject has history of penetrating keratoplasty (PKP)
- Subject underwent large incision extra capsular cataract extraction
- Subject underwent cataract phacoemulsification within the last month
- Subject has a visually significant cataract that is planned for extraction at the time of filtering surgery or within 12 months thereafter
- Any ocular disease or history in the operated eye other than glaucoma and cataract, such as uveitis, ocular infection, severe dry eye, severe blepharitis, active proliferative retinopathy, ICE syndrome, epithelial or fibrous down growth, aphakia, and ocular pathology that may interfere with accurate IOP measurements
- Subject has vitreous present in the anterior chamber for which vitrectomy is anticipated
- IOP of ≤ 18 mmHg
- Subject participates in any other concurrent ocular investigation.

9.4 Subject Enrollment

9.4.1 Informed Consent and Enrollment

The informed consent/patient information sheet written in the subject's native language will be explained to each prospective subject by the investigator or a trained clinical professional. The final informed consent form must be approved by the Institutional Review Board (IRB). Once the subject has been informed of all aspects of the study, the subject will then be given a choice to voluntarily confirm his or her participation in the study as documented by completion of the Informed Consent. After signing the Informed Consent and the HIPAA (Health Insurance Portability and Accountability Act) authorization, the subject can then proceed with the screening evaluation.

The subject has the right to withdraw from the study at any time without consequences, as indicated in the Patient Informed Consent documentation.

9.4.2 Baseline Evaluation

After obtaining an understanding of the purpose of this study, reviewing and signing the informed consent form, all potential subjects will undergo an examination in order to determine their eligibility for this study.

The screening examination will consist of applanation tonometry to measure IOP, general slit-lamp biomicroscopy to review the overall health of the eye, visual acuity (VA) measurements, and a review of current medications and prior surgeries. All information should be compared to the specific inclusion and exclusion criteria in order to determine if the subject is eligible to participate in the study.

The following criteria are provided below to assist with appropriate screening for all subjects in this study:

- **Diagnosis**

Investigator is to provide the diagnosis in each eye, as either ocular hypertension (elevated IOP without evidence of visual field loss or cupping of the optic nerve head) or glaucoma (elevated IOP with either glaucomatous visual field loss, as judged by automated threshold visual field testing, or cupping of the optic nerve head).

- **Measurement of intraocular pressure**

Each time IOP is measured, the surgeon or technician is to utilize a Goldmann tonometer, however, an independent observer should read the measurement and then record the measurement to minimize observer bias.

Two measurements should be taken and the mean recorded on the case report form UNLESS they differ by more than 2 mmHg in which case a third measurement is taken and the median value is recorded.

- **Visual Field Examination**

Visual fields must be automated threshold visual fields (e.g., 30-2 or 24-2 Humphrey). SITA Standard visual fields are required. Visual fields must be reliable, defined as less than 33% false positives, false negatives, and fixation losses.

The visual field must be performed within three to six months of study entry and meet the aforementioned requirements. Both the test eye and the fellow eye should have visual field data.

Visual fields are to be performed with a non-dilated pupil unless, in the opinion of the investigator, the pupil is so miotic that dilation is required (e.g., < 3 mm). If dilation was performed at baseline, it should be performed at all subsequent visual field examinations. However, dilation should not be performed before the IOP measurement on the appropriate visits.

For OAG subjects and in accordance with the American Academy of Ophthalmology (AAO) Preferred Practice Patterns, the severity of glaucoma damage can be assessed as follows: (1) Mild – characteristic optic nerve abnormalities are consistent with glaucoma, but there is a normal visual field and (2) Moderate – visual field abnormalities are in one hemifield and not within 5 degrees of fixation.

For OHT subjects, qualifying visual fields must be normal and reliable in the study eye.

- Cup-to-Disc Ratio

A numerical expression indicating the percentage of disc occupied by the optic cup. A score from 0.1 to 0.9 (in 0.1 increments) should be indicated.

- Visual Acuity

Best corrected visual acuity will be measured at baseline and at each follow-up visit. Visual acuity will be measured using Snellen line method.

If a subject satisfies all inclusion and exclusion criteria the subject will be enrolled into the study. The subject is then randomized to participate in either Group A or Group B using the sealed envelope method of randomization.

Group A

Subjects will undergo implantation of the Ex-PRESS mini glaucoma shunt.

Group B

Subjects will undergo standard trabeculectomy.

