9.5.2 Surgical procedure

Ex-PRESS implantation procedure

Local or topical anesthesia is administered and the eye is prepared and covered using conventional sterile procedures. Implantation is performed using a special introducer, conventional microsurgical instruments and a surgical microscope.

The Ex-PRESS, mounted on its introducer is inserted into the anterior chamber at the limbus through the sclera under the scleral flap.

The implantation procedure may be performed as follows:

1. Creation of a fornix or limbal based conjunctival flap in the upper quadrants
2. Creation of a limbal-based scleral flap extending into clear cornea
3. Delicate application of MMC solution onto the sclerectomy bed. (MMC concentration 0.4mg/ml for 1-3 minutes)
4. Penetration into the anterior chamber using a 23-25G needle, halfway between the white sclera and the clear cornea (in the center of the grey zone), and creation of a track incision at the limbus
5. Prior to implantation, a thorough mobility check should be performed
6. Implantation of the Ex-PRESS implant loaded on its introducer, through that pre-incision
7. Withdrawal of the introducer
8. Tucking the plate under the scleral flap, and verification of its position
9. Suturing the scleral flap with sutures

After the implantation procedure, antibiotics and steroids are administered topically, the eye is covered with a pad and the patient is discharged.

Standard trabeculectomy procedure

1. Creation of a fornix or limbal based conjunctival flap in the upper quadrants
2. Creation of a limbal-based scleral flap extending into clear cornea
3. Delicate application of MMC solution onto the sclerectomy bed. (MMC concentration 0.4mg/ml for 1-3 minutes)
4. Creation of fistula 1mm x 2mm in size
5. Iridectomy
6. Suturing the scleral flap
7. Repositioning of the conjunctiva with sutures

After the procedure, antibiotics and steroids are administered topically, the eye is covered with a pad and the patient is discharged.

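### Randomisation sits at the baseline evaluation and nothing withholds the arm from the surgeon, so flap type and mitomycin time can be chosen with the arm known

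*Combined protocol and SAP*

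**What the plan says.** Section 9.4.2 (Baseline Evaluation) gives the order of events: "If a subject satisfies all inclusion and exclusion criteria the subject will be enrolled into the study", followed by "The subject is then randomized to participate in either Group A or Group B using the sealed envelope method of randomization". The synopsis (9.1) and Table 1 (9.6) list screening and surgery as separate visits. The synopsis describes the design as "A prospective, two arm, active control, unmasked, randomized study".

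Section 9.5.2 lists the operative steps for each arm. Three steps are common to both:

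- Step 1: "Creation of a fornix or limbal based conjunctival flap in the upper quadrants".
- Step 2: "Creation of a limbal-based scleral flap extending into clear cornea".
- Step 3: mitomycin, "MMC concentration 0.4mg/ml for 1-3 minutes".

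The lists first differ at step 4. For the shunt it is "Penetration into the anterior chamber using a 23-25G needle"; for trabeculectomy it is "Creation of fistula 1mm x 2mm in size".

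The one measure against bias is an independent reader of the tonometer (9.4.2 and 9.6). Section 12.0 names lens status as the only covariate to be explored.

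**The concern.** Randomisation balances the arms on everything fixed before allocation. Choices made afterwards by someone who knows the arm have no such protection. Here the surgeon has two explicit options within the shared steps, the flap type and a threefold range of mitomycin time (3 / 1 = 3), and no rule for either. If surgeons lean one way for shunt eyes and another way for trabeculectomy eyes, the trial compares device plus technique, not device alone.

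Both halves of the claim in section 8.0 are exposed: superior safety, and efficacy as good as trabeculectomy. The primary effectiveness endpoint (7.1) is IOP at or below 18 mmHg at 12 months. The primary safety endpoint (7.3) includes hypotony, shallow or flat chamber and leaking bleb. The tonometer reader guards against reading bias and does nothing about operative technique.

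**Working it through.** **1. Order of events.** No figure in the plan bears on this point, so the main check is textual.

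| Event | Where | Is the arm withheld from the surgeon? |
|---|---|---|
| Eligibility, enrolment, then randomisation | 9.4.2 | Not stated |
| Separate surgery visit | 9.1; 9.6, Table 1 | Not stated |
| Steps 1-3, same wording in both arms | 9.5.2 | Not stated; design is unmasked |
| Step 4 onward, arm-specific | 9.5.2 | Cannot be withheld |

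For steps 1-3, prior knowledge of the arm is possible and partly avoidable. From step 4 it is unavoidable.

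**2. What a small technique effect would do to the success rate (illustration).** Assume that 12-month IOP is normal with mean 13 to 15 and SD 3 to 5 mmHg, and that technique raises IOP by 1 mmHg in one arm. None of these values is in the documents.

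Success = Φ((18 − mean) / SD); after the shift, Φ((18 − mean − 1) / SD).

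- Mean 14, SD 4: Φ(1.00) = 84.1%; Φ(0.75) = 77.3%; loss 6.8 points.
- Mean 13, SD 3 (smallest loss): Φ(1.667) = 95.2%; Φ(1.333) = 90.9%; loss 4.3 points.
- Mean 15, SD 3 (largest loss): Φ(1.00) = 84.1%; Φ(0.667) = 74.8%; loss 9.4 points before rounding.

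**3. What such a shift would do to the test (illustration).** From the plan: 60 per arm (9.3.1) and Fisher's exact test (12.0). Assumed: two-sided alpha 0.05, because 12.0 states none; the base rates; and no device effect. The rejection probability is the sum, over all pairs of event counts (a, b), of Bin(a; 60, p1) × Bin(b; 60, p2) wherever the Fisher p-value is at most 0.05.

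| Base rate in one arm | Shift 0 | 5 points | 10 points | 15 points |
|---|---|---|---|---|
| Success 70% (raised) or hypotony 30% (lowered) | 3.1% | 6.3% | 18.1% | 41.8% |
| Success 80% (raised) or hypotony 20% (lowered) | 2.8% | 7.0% | 24.7% | 62.7% |

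Each row covers both endpoints because the test is symmetric in event and non-event. Once there is a shift, nearly all rejections fall in its direction. The table shows what a shift would do if it occurred; it is not evidence that one would.

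**The case against.** Four objections carry weight.

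**Opening time.** A reader might infer that the plan has the envelope opened at enrolment. The text does not say when it is opened, by whom, or whether the operating surgeon sees it. That stands. What remains is that early opening is the natural reading and nothing prevents it.

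**Shared wording is not shared technique.** A reader might infer that nothing in steps 1-3 depends on the arm, so that any difference there is confounding. The protocol does not support this. Section 4.0 lists a smaller conjunctival incision than trabeculectomy among the shunt's potential benefits. Step 8 of the shunt list places a plate under the scleral flap, and that list is worded as permissive. Some flap difference may belong to the procedure under test. That stands, and it makes opening the envelope after step 3 a debatable remedy. It does not explain an arm-dependent mitomycin time.

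**Partial reach.** The surgeon knows the arm while suturing the flap, prescribing hypotensive medication and arranging extra visits, and success counts with or without medication. That stands. Only the avoidable part is at issue.

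**No evidence of effect.** Nothing in the documents ties these choices to an IOP shift or suggests that surgeons would choose differently by arm. That stands. It also goes too far to say that analysis could do nothing. If flap type and exposure time are recorded, they can be compared by arm and examined in sensitivity analyses, though imperfectly. CRF 2 (10.3) may already capture them, since its fields are not shown.

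**Conclusion.** The point holds in a limited form. As written, the plan lets an unmasked surgeon know the arm when choosing flap type and mitomycin time, and its only safeguard does not cover those choices. This rests on reading 9.4.2 in its natural order. If opening in theatre was intended, the text still needs to say so.

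The size is unknown. Under the stated assumptions, a 1 mmHg shift moves success by 4.3 to 9.4 points, and a shift of 5 to 10 points takes false rejection from about 3% to 6-25%. The documents support neither a particular shift nor a direction.

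A reader might go further and conclude that both primary endpoints are biased throughout. That does not follow. The documents show a route for bias and no bias, and vitreous loss and hyphema are less plausibly affected by steps 1-3 than hypotony, shallow chamber or leak. A cheap preventive change is justified; a claim that the comparison is invalid is not.

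**What to change.** 1. In 9.4.2, state that the envelope is opened only after the surgeon has recorded on CRF 2 the intended flap type and mitomycin exposure time for that eye, and as close to surgery as practical, for example on the day. State who opens it.
2. On CRF 2, record the actual flap type and exposure time, and the reason for any departure from the recorded intention.
3. In section 12.0, add a report of intended and actual choices by arm.
4. Reconcile the shared wording of steps 1-3 in 9.5.2 with the smaller conjunctival incision in section 4.0. Opening the envelope after step 3 is an option only if the sponsor confirms that the flaps do not need to differ by arm.

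No flap type or exposure time is proposed; the request concerns when the choice is recorded.

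The cost is a protocol amendment, one extra CRF entry before opening, and later notice to the subject and the theatre of the assigned procedure. It needs no extra staff, visit or test. A recorded intention does not stop a surgeon from departing from it, but it makes departures visible by arm.
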